3.2.2 Key secondary endpoints

3.2.2.1 Change from baseline in pre-BD FEV₁

Pre-BD FEV₁ will be determined by spirometry at the clinic visit. Change from baseline is obtained as an absolute difference between Week 52 measure and the baseline value as defined in [Section 3.1.1](#). Changes from baseline at other post-baseline time points will be calculated similarly.

Only those spirometry tracings determined to be acceptable or borderline will be used. The best (highest) FEV₁ will be derived from the available individual acceptable or borderline FEV₁ measurements at each visit.

3.2.2.2 Change from baseline in AQLQ(S)+12 total score

In the AQLQ(S) +12 the subjects are asked to recall their experiences during the previous 2 weeks and to score each of the 32 questions on a 7-point scale ranging from 7 (no impairment) to 1 (severe impairment).

The total score is calculated as the mean response to all questions. The 4 individual domain scores (4 domains assessing 1) symptoms, 2) activity limitations, 3) emotional function, and 4) environmental stimuli) are the means of the responses to the questions in each of the domains. The following are the question numbers on the AQLQ(S) +12 questionnaire relating to each domain:

Table 4 AQLQ(S)+12 domains

Domain	AQLQ(S)+12 question number
Symptoms	6, 8, 10, 12, 14, 16, 18, 20, 22, 24, 29, 30
Activity Limitations	1, 2, 3, 4, 5, 11, 19, 25, 28, 31, 32
Emotional Function	7, 13, 15, 21, 27
Environmental Stimuli	9, 17, 23, 26

If response to any of the questions is missing, the total score will be missing. If response to a question within a domain is missing, the score for that domain will be missing.

The key secondary endpoint for the AQLQ(S) +12 will be the change in total score from baseline at Week 52. Change from baseline in each domain will also be calculated. The definition of baseline is given in [Section 3.1.1](#). Changes from baseline at other post-baseline time points will be calculated similarly.

3.2.2.3 Change from baseline in ACQ-6 score

The ACQ-6 questionnaire includes questions on:

1. Awakening at night by symptoms
2. Limitations of normal daily activities
3. Waking in the morning with symptoms
4. Dyspnoea
5. Wheeze
6. Daily rescue medication

The questions of the ACQ-6 are measured on a 7-point scale scored from 0 (totally controlled) to 6 (severely uncontrolled). The ACQ-6 score is computed as the unweighted mean of the responses to the 6 questions. If response to any of the questions is missing, the ACQ-6 will be missing.

The key secondary endpoint for the ACQ-6 will be the change in mean score from baseline at Week 52, where baseline is as defined in [Section 3.1.1](#). Change in mean score from baseline at other post-baseline time points will be calculated similarly.

3.2.2.4 Change from baseline in weekly mean daily Asthma Symptom Diary score

Asthma symptoms during night-time and daytime will be recorded by the subject each morning and evening in the Asthma Symptom Diary (ASD). Symptoms will be recorded using a scale 0-4, where 0 indicates no asthma symptoms. Asthma symptom daytime score (recorded in the evening), night-time score (recorded in the morning), and total (daily) score will be calculated separately.

The daily ASD score will be calculated by taking the mean of the 10 component items recorded in the evening and the morning. The daytime ASD score is defined as the mean of 5 items recorded in the evening and the night-time ASD score is the mean of 5 items recorded the following morning (i.e. the measurements recorded in the evening and on the following morning are used in the calculation of the daily ASD score). If a subject is missing one or more of the 5 items for either night-time or daytime asthma symptom score on a given day (evening followed by morning), then the total score for that day will be set to missing. If all 5 items are present, then the daytime/night-time ASD score (as applicable) will still be calculated.

Weekly mean scores and changes from baseline for daytime, night-time, daily scores and individual items will also be calculated. Weekly mean scores for baseline are defined in [Section 3.1.1](#). For the Week 1 mean post-baseline, the week will start with the evening

measurement on the day of randomisation and will end with the morning measurement one week later (i.e. 7 daily pairs, where one day is defined as evening followed by morning). If more than 3 days are missing, then the Week 1 mean will be missing. Weekly mean scores for all subsequent weeks will be defined similarly, with the same rule for handling missing days.

It is expected that subjects will complete the ASD once in the evening and once in the morning. In the event that multiple evening measurements and/or multiple morning measurements are recorded on a particular day, then the first evening and/or first morning measurement respectively will be used for all derivations required for analysis.

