7.1.1 Procedures for discontinuation of study treatment

Subjects are free to discontinue IP or withdraw from the study at any time without prejudice to further treatment. Discontinuing study treatment is not the same as study withdrawal. Procedures to follow for study withdrawal are detailed below in section 7.3. If the subject decides to withdraw consent, then the reason for this must be recorded separately in the eCRF.

A subject that decides to discontinue IP should always be asked about the reason(s) and the presence of any adverse events. The reason for discontinuing treatment and the date of last IP administration should be recorded in the eCRF. Subjects permanently discontinuing IP administration should be given locally available standard of care therapy, at the discretion of the Investigator. However, treatment with marketed or investigational biologics is not allowed until week 64 even if the subject has discontinued IP. Interaction studies between tezepelumab and other biologics indicated for the treatment of asthma have not been conducted. For additional information regarding pharmacokinetic and pharmacodynamic effects of tezepelumab reference should be made to the investigator brochure.

All subjects who prematurely discontinue IP should return to the study center and complete the procedures described for the premature IP Discontinuation visit (IPD) at 4 weeks (+/-5 days) post last IP administration. Subjects who discontinue treatment should be encouraged to return for all regularly scheduled visits for safety and efficacy assessments.

At the IPD visit the subject will be given three options as to how they will be followed as follows:

1. The subject should be encouraged to return for all regular clinic visits and perform all scheduled assessments until he/she completes a total of 52 weeks treatment period.
2. The subject will be offered follow-up on a monthly basis via telephone calls while continuing diary and ePEF completion (no further procedures will be performed), until the subject completes 52 weeks in the study. In addition to the PRO assessments that are performed at home, the subject may also complete the other clinic specified PRO assessments (as defined in the SoA) at home as well. The subject should return for a follow-up visit 16 weeks (+/- 5 days) (refer to SoA, V19 – Week 64) post last IP administration and for the EOT visit at Week 52 (+/-5 days).

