8.1.6.1 Daily Diary

The daily diary will be completed each day from the evening of Visit 2 or Visit 2a to the morning of Visit 17. The morning eDiary will include: Asthma Symptom Diary (ASD) morning items, questions about rescue medication, nighttime awakening, and use of maintenance medications. The evening eDiary will include: ASD evening items and questions about rescue medications. Upon completion of the morning and evening questions the subject will complete the peak expiratory flow assessment.

There will be triggers in the ePRO device to alert the subjects to signs of worsening of asthma and to contact their physician, please refer to section 8.1.1. The subject should contact the investigator for evaluation after receiving a diary alert.

ASD

Asthma symptoms will be recorded using the ASD ([Globe et al 2015](#)), which comprises 10 items (5 items in the morning; 5 items in the evening). The morning items assess nighttime symptom severity in relation to wheezing, shortness of breath, cough, and chest tightness, and the frequency of nighttime awakening. The evening items assess symptom severity in relation to wheezing, shortness of breath, cough, and chest tightness, and activity limitation since waking. Items are scored from "0" (no symptom, no nighttime awakening, or no activity limitation) to "4" (very severe symptom, unable to sleep, or extreme activity limitation). A daily ASD score is

the mean of the 10 items. Responses for all 10 items are required to calculate the daily ASD score; otherwise, it is treated as missing. Calculation of a daily ASD score requires data from the evening diary assessment and the subsequent morning diary assessment. For the 7-day average asthma symptom score, scoring is done with no imputation using the mean of at least 4 of the 7 daily ASD scores as a mean weekly item score. The 7-day average ASD score ranges from 0 to 4.

Global asthma symptom items

In addition to the ASD, subjects will complete a single item global assessment of asthma symptoms (0-3) each morning and evening. The sum of evening and subsequent morning single global item scores (0-6) will be used for the alerts system.

Rescue medication

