3.1.5 Visit windows

All summaries and analyses, both efficacy and safety, which are presented by time point (e.g. “Week 52”) will use a visit window to classify the data record, which is derived from the assessment date relative to the reference start date. This approach allows appropriate classification of visits which may have occurred significantly earlier or later than the protocol assessment schedule, as well as the use of data captured at visits which have no fixed timing (notably the IPD visit), and the handling of data captured at visits for which the database label is incorrect and unresolvable.

Nominal database visit numbers will not be used in any summary or analysis by visit.

For efficacy variables, the reference start date is the date of randomisation, and relative day is therefore defined as $(Date\ of\ assessment - Date\ of\ randomisation) + 1$.

For safety variables, the reference start date is the date of first dose of IP, and relative day is therefore defined as $(Date\ of\ assessment - Date\ of\ first\ dose\ of\ IP) + 1$.

Any data collected at unscheduled or repeat visits will be listed and will be included in baseline definitions (see [Section 3.1.1](#)), and in any definitions of maximum value, minimum value or last value within the relevant study period.

Data collected at unscheduled or repeat visits will also be included in visit windows, and therefore may be included in summaries or analyses by visit or used in any sensitivity analyses which involve imputation of data from subjects with non-missing values to subjects with missing values. In the case of a missing value at a scheduled visit, which is then followed by a non-missing value at an unscheduled or repeat assessment within the same visit window, the non-missing value at the unscheduled/repeat assessment will replace the missing value at the scheduled visit.

If a subject has more than one non-missing value within the same visit window, the following rules will apply:

- The non-missing value closest to the target day will be selected for analysis at that visit
- If two non-missing values are the same distance from the target day, the earlier of the two values will be selected for analysis at that visit
- If two non-missing values are recorded on the same day and have a different assessment time associated with both of them, the value with the earliest assessment time will be selected for analysis at that visit.

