- If two non-missing values (for continuous variables) are recorded on the same day and have no assessment time associated with at least one of them, or the same assessment time associated with both of them, the average of the two values will be selected for analysis at that visit. For categorical variables in this situation, the worst case will be used.
- If there are multiple ADA samples in the same visit window with both positive and negative results, the sample with a positive result and the highest titer value should be selected.

If a subject has no value within a particular visit window, then the subject will have a missing value at that visit in summaries and analysis.

The same visit window definitions below will be used regardless of whether the planned treatment period or the on-treatment period is used for analysis (see [Section 3.1.4](#)). In practice, each data record in the planned treatment period will be first identified, and then further flagged according to whether it is on-treatment or off-treatment. This flag will be used to select all eligible records for subsequent visit windowing, according to whether the derived visits are to be used in a planned treatment period or an on-treatment period analysis. It should be noted that, if treatment was discontinued within a particular visit window, the rules above for handling multiple values within the same visit window could select a different record according to whether a planned treatment period analysis or an on-treatment period analysis is needed.

Table 1 summarises the visit windows to be used for all variables unless specified otherwise. It corresponds to the full (mostly 4-weekly) protocol scheduling for clinic visits, and will be used for all variables by default, including those variables which are not captured at every clinic visit, unless it is indicated below that the visit windows in Table 2 or Table 3 should be used.

Table 1 Visit windows – all variables where not specified otherwise

Time Point	Target Day	Visit Window
Baseline (Week 0)	1	See Section 3.1.1 for baseline definitions
Week 2	15	2-21
Week 4	29	22-42
Week 8	57	43-70
Week 12	85	71-98
Week 16	113	99-126
Week 20	141	127-154

Time Point	Target Day	Visit Window
Week 24	169	155-182
Week 28	197	183-210
Week 32	225	211-238
Week 36	253	239-266
Week 40	281	267-294
Week 44	309	295-322
Week 48	337	323-350
Week 52	365	351-378
Follow-up Week 58	407	379-427
Follow-up Week 64	449	428-469

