Table 2 summarises the visit windows which will be used for EQ-5D-5L, for which more frequent completion (every 2 weeks) is scheduled in the protocol.

Table 2 Visit windows – EQ-5D-5L only

Time Point	Target Day	Visit Window
Baseline (Week 0)	1	See Section 3.1.1 for baseline definitions
Week 2	15	2-21
Week 4	29	22-35
Week 6	43	36-49
Week 8	57	50-63
Week 10	71	64-77
Week 12	85	78-91
Week 14	99	92-105
Week 16	113	106-119
Week 18	127	120-133
Week 20	141	134-147
Week 22	155	148-161

Time Point	Target Day	Visit Window
Week 24	169	162-175
Week 26	183	176-189
Week 28	197	190-203
Week 30	211	204-217
Week 32	225	218-231
Week 34	239	232-245
Week 36	253	246-259
Week 38	267	260-273
Week 40	281	274-287
Week 42	295	288-301
Week 44	309	302-315
Week 46	323	316-329
Week 48	337	330-343
Week 50	351	344-357
Week 52	365	358-371

Table 3 summarises the visit windows which will be used for those variables for which the most sparse scheduling is planned in the protocol. These variables are: weight, height (adolescents only), SGRQ score, SNOT-22 score, WPAI+CIQ scores and post-BD spirometry.

Table 3 Visit windows – sparse protocol schedule

Time Point	Target Day	Visit Window
Baseline (Week 0)	1	See Section 3.1.1 for baseline definitions
Week 24 (not SNOT-22)	169	141-196
Week 28 (SNOT-22 only)	197	169-224
Week 52	365	337-392

In all cases above, no time points will be presented in summary tables or included in statistical analysis which do not correspond to the time points scheduled in the protocol for the variable in question. Listings of data will include all scheduled and unscheduled visits, including derived weekly means for data recorded beyond the final scheduled visit for all subjects randomised.

Data from the extension study (for participating subjects) will not be used for any of the visit window classifications above.

Finally, it should be noted that a visit window approach will not be used for data captured on a device daily by the subject, which will be aggregated for analysis at each relevant time point by using a weekly mean or similar approach. For this purpose, the definition of the weekly mean is provided in the relevant endpoint derivation sections of this SAP.

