3.2.4 Other secondary endpoints

3.2.4.1 Other exacerbation endpoints

Time from randomisation to the first asthma exacerbation will also be used as a supportive endpoint to the primary objective, and is calculated as follows:

$$\text{Time to 1}^{\text{st}} \text{ exacerbation (days)} = [\text{Start date of 1}^{\text{st}} \text{ exacerbation} - \text{date of randomisation}] + 1.$$

Subjects without an exacerbation will be censored on the date of last exacerbation assessment, as defined in [Section 3.2.1](#).

Time from randomisation to first asthma exacerbation due to hospitalisations or ER visits will also be calculated, similarly to above.

The proportion of subjects who had no asthma exacerbations during the planned treatment period will also be calculated. A subject will be considered to have completed the planned treatment period, if the planned treatment period is greater than 359 days (Day 364 minus 5, to account for visit windowing).

- Subjects who had no asthma exacerbations during the planned treatment period and who completed the planned treatment period (to Week 52) will be defined as exacerbation free [a].
- Subjects who did not complete the planned treatment period will be defined as not having a successful outcome for this endpoint [b] [c].
- Subjects who did not complete the planned treatment and had an asthma exacerbation will be defined as not having a successful outcome for this endpoint [d].

	No exacerbation	Exacerbation
Completed planned treatment period	[a] Exacerbation free/successful outcome	[d] No successful outcome
Did not complete planned treatment period	[b] No successful outcome	[c] No successful outcome

The proportion will be calculated for each treatment group as:

Number of subjects who were exacerbation free [a] / number of subjects in treatment group.

The proportion of subjects free from exacerbations that required hospitalisation or ER visits during the planned treatment period will also be calculated similarly. A subject who only had an exacerbation which did not lead to hospitalisation or ER visit will be considered a successful outcome for this endpoint.

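### A subject still in the study whose Visit 17 falls on Day 360 or 361 has no Week 52 ASD mean even with a complete diary; a narrow fallback rule would recover it

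*SAP*

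**What the plan says.** SAP 3.2.2.4 starts diary Week 1 on the evening of randomisation and gives it seven evening-morning pairs. A week with more than three days missing has no mean. For the rest of the year, "Weekly mean scores for all subsequent weeks will be defined similarly, with the same rule for handling missing days". Protocol 8.1.6.1 sets the same minimum: "scoring is done with no imputation using the mean of at least 4 of the 7 daily ASD scores".

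The diary has a fixed end: "The daily diary will be completed each day from the evening of Visit 2 or Visit 2a to the morning of Visit 17". The protocol's Table 2 gives Visit 17 a window of 5 days either side of Week 52, and Protocol 7.1.1 repeats it "for the EOT visit at Week 52 (+/-5 days") for subjects off treatment. SAP 3.1.4 ends the planned treatment period on the date of the Week 52 visit.

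Clinic measurements are windowed by date. SAP 3.1.5 explains: "This approach allows appropriate classification of visits which may have occurred significantly earlier or later than the protocol assessment schedule". It adds: "Table 1 summarises the visit windows to be used for all variables unless specified otherwise". That table assigns Days 351 to 378 to Week 52. Diary data are excluded: "a visit window approach will not be used for data captured on a device daily by the subject". SAP 3.2.4.1 does allow for early visits when it defines completion of the planned treatment period as more than 359 days ("Day 364 minus 5, to account for visit windowing").

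SAP 4.2.5.1 names the expected sources of missing key secondary data: loss to follow-up, death, withdrawal of consent, follow-up Option 3, and Option 2 for FEV1 only.

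**The concern.** Each rule is reasonable alone. Together they make a Week 52 ASD value impossible for some subjects who did everything asked of them. Week 52 is the time point tested in H05. The same attendance supplies valid Week 52 values for the other three key secondary endpoints, so the gap is specific to the diary. It is not among the sources of missing data in SAP 4.2.5.1.

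Home PEF ends on the same morning and follows similar weekly rules (Protocol 8.1.3, SAP 3.2.4.4), so it has the same gap. So do the other weekly eDiary means in SAP 3.2.4.3. The effect on night-time awakenings is less clear, because that endpoint is a percentage of available nights.

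At stake are a little precision for H05 and the affected subjects' values in the Week 52 descriptive ASD, responder, PEF and eDiary summaries.

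**Working it through.** **Plan's own figure.** Inputs from SAP 1.3: 530 per arm, difference 0.3, SD 1.3, two-sided 5%. Power = Φ(0.3 / (1.3 × √(2/530)) − 1.96) = Φ(3.757 − 1.96) = 96.4%, against a stated 95% or higher. The minimum detectable difference is 1.96 × 1.3 × √(2/530) = 0.157, against a stated 0.16. Both reproduce.

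**Day count.** Randomisation is Day 1 and the Week 52 target is Day 365 (SAP 3.1.5), so the window is Days 360 to 370. Week w holds the pairs starting on the evenings of Days 7(w − 1) + 1 to 7w. For w = 52 that is Days 358 to 364, with the last morning on Day 365. With Visit 17 on Day D, complete pairs = min(7, D − 358):

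| Visit 17 day | Pairs | Week 52 mean |
|---|---|---|
| 360 | 2 | missing |
| 361 | 3 | missing |
| 362 | 4 | present, no spare day |
| 363 | 5 | present |
| 364 | 6 | present |
| 365–370 | 7 | present |

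Counted separately, mornings and evenings for home PEF each also give D − 358 up to Day 365.

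**How many subjects (assumed).** The documents give no visit timing. Take visit days as normal around Day 365, restricted to the window, among 1060 × 0.9 = 954 attenders (the plan's 10% dropout). The share on Days 360–361 is then 0.9% (about 8 subjects) with an SD of 1.5 days, 3.6% (34) with an SD of 2, and 9.4% (90) with an SD of 3. An even spread gives 2/11 = 18% (173), as an illustration only.

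**Effect on H05.** Suppose a fraction f lacks Week 52 and the model borrows from Week 51 with correlation r. The effective size per arm is 530 / [(1 − r²)/(1 − f) + r²].

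| f | n, r = 0.7 | power | n, r = 0.9 | power |
|---|---|---|---|---|
| 0.9% | 527.6 | 96.3% | 529.1 | 96.4% |
| 3.6% | 520.1 | 96.1% | 526.3 | 96.3% |
| 5% | 516.1 | 96.0% | 524.8 | 96.2% |
| 9.4% | 503.4 | 95.6% | 519.8 | 96.1% |

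The standard error rises by 0.5–1.3% at f = 5% and by 1.0–2.6% at f = 9.4%. For a given r these overstate the loss, because the MMRM borrows from all earlier weeks. With the even-spread 18%, the same formula gives n = 476.0 and 94.5% (r = 0.7), or 508.5 and 95.7% (r = 0.9).

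**What a fallback recovers.** Use the 7 pairs ending on the morning of the visit when the fixed block has fewer than 4 valid pairs. Assume independent daily compliance and an SD of 2 days. Attenders without a Week 52 mean fall from 5.1% to 0.02% at 95% compliance, and from 7.3% to 0.3% at 90%. This includes subjects seen on Days 362–364 who missed an entry, as well as the certain losses on Days 360–361.

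**The case against.** The main analysis already copes. SAP 4.2.5.1 fits all 52 weekly means by direct likelihood, so these subjects contribute Weeks 1 to 51. The fixed grid is a defensible choice: one definition for every week and no diary day used twice. The 4-of-7 minimum is the protocol's own scoring rule. All of this stands, and it is why the point is minor.

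A loosely worded remedy could also do more harm than the gap. Protocol 7.1.1 and 7.3 have subjects who withdraw early complete the EOT visit. A rule triggered by any visit before Day 365 could turn a withdrawer's last diary week into a Week 52 value. That would contradict the missing-at-random analysis and pre-empt the sensitivity imputations in SAP 4.2.5.2. On Day 358 the trailing week would be identical to Week 51. This objection also stands, and any fallback must be bounded accordingly.

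A reader might go further and infer that H05 is biased or underpowered, or that up to 18% of subjects are lost. The documents do not support that. Nothing in them links early attendance to treatment. The subjects are not dropped from the model. The 18% comes from an even spread chosen for illustration; it is neither an estimate nor an upper bound.

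**Conclusion.** The gap is real and follows from date arithmetic alone: a non-withdrawn subject seen on Day 360 or 361 cannot have a Week 52 ASD mean. Its consequence is small. For assumed shares of 0.9% to 9.4% and assumed correlations of 0.7 to 0.9, power for H05 stays between 95.6% and 96.4%, above the stated 95%. No material bias is expected. What is certainly absent is these subjects' Week 52 value in the descriptive and responder summaries, although their last diary days were collected. Confidence is high in the day count. How many subjects are affected rests on assumption.

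**What to change.** Add to SAP 3.2.2.4 a rule for subjects who have not withdrawn from the study and whose Week 52 visit falls on Days 360 to 364. If their fixed Week 52 block has fewer than 4 valid pairs, the Week 52 mean is taken over the 7 evening-morning pairs ending on the morning of that visit, with the same 4-day minimum. In every other case the fixed-week value, or missing, is kept. State that EOT visits done at early withdrawal or before Day 360 never trigger the rule. Identify the visit by its date, since SAP 3.1.5 does not use nominal visit numbers for by-visit analyses.

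Apply the same rule to the other weekly eDiary means, and to home PEF using the 7 mornings or 7 evenings separately. Add early in-window visits to the sources of missing data in SAP 4.2.5.1.

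The cost is a few lines of SAP text and derivation code, settled before unblinding. No valid fixed-week value changes. The downside is overlap with Week 51 of 365 − D diary days: 5 on Day 360, 4 on Day 361, and 3, 2 or 1 on Days 362 to 364 when the rule is triggered. This raises the Week 51–52 correlation for those few subjects within a common covariance matrix.
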